## 5.0 SUBJECT DISPOSITION

Subject disposition will be summarized overall for all subjects who entered the study in a disposition table (i.e., signed the informed consent for the study). In addition, the number of subjects in each population (ITT and PP) and subjects that were removed from a population will be summarized. The number and proportion of subjects who complete the study, as well as those who discontinue the study will be summarized along with the reason for discontinuation.

Primary reason for treatment termination include the following criteria:

- Withdrawal of consent for further treatment
- Pregnancy or intent to become pregnant
- DLT at any time
- Progressive disease requiring alternative systemic treatment
- Significant protocol violation or noncompliance that, in the opinion of the Investigator or Sponsor, warrants withdrawal
- Development of intercurrent, non-cancer-related illnesses or complications that prevent either continuation of therapy or regular follow-up
- Best medical interest of the subject (at the discretion of the Investigator)

Primary reason for study discontinuation include the following criteria:

- Best medical interest of the subject at the discretion of the Investigator
- Initiation of alternative anticancer therapy (marketed or investigational)
- Withdrawal of consent for all follow-up
- Lost to follow-up
- Death

Subject disposition data will also be presented in data listings.

## 6.0 DEMOGRAPHIC AND BASELINE CHARACTERISTICS

### 6.1 Demographic Characteristics

Demographic and baseline characteristics at study entry (Screening/baseline visit which will occur up to one month before start of treatment) will be summarized for the ITT and PP Populations.

Demographic and baseline variables to be summarized include:

- Continuous variables
  - Age (years) at time of consent
  - Height (cm) at screening
  - Weight (kg) at screening
  - Body mass index (BMI) ( $\text{kg}/\text{m}^2$ ) at screening
- Categorical variables
  - Gender
  - Race
  - Ethnicity

Demographic and baseline characteristics by subject will be presented in a table and data listings.

### 6.2 Medical History

Medical History was collected at the Screening/Baseline visit. Medical history, including any ongoing and significant conditions or diseases that stopped at or prior to informed consent, must be elicited from each subject during screening. The medical history shall include a complete review of systems, past medical and surgical histories, and any allergies.

The frequency count and percentage of subjects experiencing any medical conditions will be tabulated by system organ classifications (SOC) and preferred term (PT). If a preferred term or system organ class was reported more than once for a subject, the subject would only be counted once in the incidence for that preferred term or system organ class.

Medical history data will also be listed for Safety Population.

### 6.3 Prior and Concomitant Medications and Procedures

Prior medications and procedures include any medication or non-drug therapy or procedure taken or performed within 30 days prior to screening and before the first dose of study drug. Prior medications will be coded using the World Health Organization Drug Dictionary [10].

Concomitant medications are all medications, other than the study drug, taken on or after the first day of study drug dose through 30 days after end of treatment. Concomitant medications and procedures will be coded using the World Health Organization Drug Dictionary.

Medications that started before the first dose of study drug and were ongoing on the date of the first dose will be considered concomitant medications.

The number and proportion of the subjects who took each medication, or had qualifying concomitant procedures, will be tabulated by the ATC-2 level and preferred name for concomitant medications. A subject will only be counted once within each ATC-2 code and within each preferred name.

Prior and concomitant medications will also be listed for ITT.

## 7.0 EFFICACY ANALYSIS

Tumor Response will be summarized and analyzed descriptively for each arm for the ITT and PP populations.

### 7.1 Response Rate

- Responses at Week 8 and Week 24 will be presented. The Number and Percent of subjects in each category (Complete Response, Partial Response, Stable Disease, Progressive Disease or Not Evaluable) will be presented.
- Best Overall Response (BOR) will also be presented. In the determination of BOR, any subsequent scans on or after the date of a clinical progression will be ignored.

### 7.2 Objective Response Rate (ORR)

- Objective Response Rate (ORR) is defined as the percentage of subjects meeting criteria of Complete Response (CR) or Partial Response (PR).
- To be assigned a status of a CR or PR, changes in tumor measurements must be confirmed by repeat assessments that must be performed at least 4 weeks after the criteria for response are first met. If a response is not confirmed, it is considered stable disease.
- If a subject had clinical progression (CP), any recorded response (CR or PR) after the date of CP will be considered invalid.

- Subjects who drop out prior to having a response assessment (including clinical progression) for ORR will be considered as non-responders and they will be included in the denominator when calculating the proportion.
- A 95% Confidence Interval based on binomial distribution will be constructed for the estimated ORR at 8 and 24 weeks.

### 7.3 Disease Control Rate (DCR)

- Disease Control Rate (DCR) is defined as the percent of subjects with Stable Disease (SD), Partial Response (PR) and Complete Response (CR).
- Subjects who drop out prior to meeting the responder criteria for DCR will be considered as non-responders.
- A 95% Confidence Interval based on binomial distribution will be constructed for the estimated DCR at 8 and 24 weeks.

### 7.4 Progression-free Survival (PFS)

- PFS is the interval between the date of first dose to the date of earliest determination of Progressive Disease (PD) (including clinical progression), or to the date of death, if PD does not occur.
- Subjects without documentation of progression at the time of the analysis will be censored at the date of last response assessment.
- Subjects with no tumor response assessment will be censored at the start date of the treatment.
- Subjects who discontinued treatment or withdrew from the study for reasons other than documented PD (including clinical progression) or death will be censored at the date of last response assessment prior to discontinuation or withdrawal.

Descriptive analyses of PFS, at Week 8, Week 24 and Overall, will include the following:

- Number and percentage of subjects that died or had a progressive disease or clinical progression,
- Number and percentage of subjects censored:
  - Number and percentage of subjects lost to follow up (unknown survival and/or progression status)
  - Number and percent of subjects survived without progression
  - Number and percentage of subjects missing tumor response assessment.

- Number and percent of subjects with initiation of alternative therapy.
- The 25th percentile, Median and 75th percentile and the maximum and minimum PFS at Week 8, Week 24 and Overall and the corresponding 95% CIs will be displayed.
- PFS rate at Week 8, Week 24 and Overall and the corresponding 95% CIs will be displayed.

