### 4.2 Per-Protocol Population (Clinical Efficacy)

The Per-Protocol (PP) Population (Clinical Efficacy) is defined as all subjects who received at least 75% of the scheduled doses of durvalumab and tremelimumab and at least 4 of the 5 BI 1361849 vaccinations over the first 2 cycles, as well as, respective disease assessments (irRECIST or RECIST, clinical progression or death), without major protocol violations. Efficacy analyses will also be presented for PP population.

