### 7.6 Duration of Response (DoR)

- Duration of response (DOR) will be calculated interval between the date of earliest determination of CR or PR to the date of first PD, clinical progression or death whatever occurs first. Patients who had a response and did not lose it subsequently and were alive will be censored at the time of last available tumor assessment.
- $DOR \text{ in weeks} = (\text{Earlier of Date of PD or death} - \text{date of first response} + 1) / 7$
- The median DOR with 2-sided 95% confidence intervals will be presented for subjects who have a confirmed CR or PR at 8 and 24 weeks.

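### The PFS censoring rules make no exception for death before the first scan, and two confidence-interval methods are named for the same PFS rate

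*SAP*

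**What the plan says.** **Event.** SAP 7.4 runs PFS from first dose to the earliest determination of PD ("including clinical progression), or to the date of death, if PD does not occur"). Protocol 4.2.1.4 gives the same definition without naming clinical progression. Neither requires that a scan was done before a death can count.

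**Censoring.** SAP 7.4 then lists three rules, which Protocol 4.2.1.4 also contains in substance:
- The first covers anyone whose progression is undocumented when the analysis is run. The cut is made at their latest assessment.
- The second covers anyone never scanned. It reads: "Subjects with no tumor response assessment will be censored at the start date of the treatment".
- The third covers early leavers. It cuts them at the latest assessment before they left, unless they left because of PD or death.

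Only the third makes an exception for death. No order of precedence is given.

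**Table rows.** SAP 7.4 plans an event row, "Number and percentage of subjects that died or had a progressive disease or clinical progression", and, among the censored categories, "Number and percentage of subjects missing tumor response assessment".

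**Related wording.** The duration-of-response rule in SAP 7.6 does write the condition out: "Patients who had a response and did not lose it subsequently and were alive will be censored". SAP 4.2 accepts death as a disease assessment for per-protocol membership: "respective disease assessments (irRECIST or RECIST, clinical progression or death".

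**Interval.** SAP 3.1 and Protocol 4.2.2 each call for a 95% binomial interval for the PFS rate at 8 and 24 weeks. Each then says that the same rate and its interval come from Kaplan-Meier estimates. SAP 7.4 promises 95% intervals without naming a method. SAP 7.7 places PFS, OS and DoR under Kaplan-Meier. SAP 7.2 and 7.3 give binomial intervals for ORR and DCR.

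**The concern.** A subject who dies before the Cycle 3 Day 1 scan is an event by definition and is censored at day 0 by the no-assessment rule. The same subject fits both the event row and the missing-assessment row. Two programmers following the text could therefore report different rates from the same data. Under the literal reading, deaths before the first scan vanish from the 8- and 24-week rates, although such a death is plainly a PFS failure.

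A death without PD after a scan meets a similar problem under the rule for undocumented progression. Clinical progression before any scan is also exposed in SAP 7.4. SAP 7.2 appears to treat clinical progression as a response assessment, but 7.4 does not carry that over.

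On the interval, a binomial calculation needs a fixed denominator. Once subjects are censored before the landmark, a programmer must either count them as failures or drop them. Both choices can depart from the Kaplan-Meier estimate itself, not only from its interval.

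**Working it through.** **Inputs.** There are 20 subjects per arm (Protocol 3.1.6). The first on-treatment scan is at Cycle 3 Day 1 (flowchart, Protocol 3.2). The documents give no counts of early deaths or PD, so all such counts below are assumptions.

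**The plan's own figure.** The table in Protocol 3.1.6 gives 12/20 = 0.60 with Clopper-Pearson limits (0.36054, 0.80881). Recomputing from beta quantiles returns 0.36054 and 0.80881. All 19 rows agree to within 0.000005.

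**Deaths before the first scan.** Let k subjects die before the scan, let m have PD at it, and let there be no other censoring.
- Deaths as events: S = (20-k-m)/20
- Deaths censored at day 0: S = (20-k-m)/(20-k)
- Ratio of second to first: 20/(20-k), which is 1.053, 1.111 and 1.176 for k = 1, 2, 3

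Week 8 rate with m = 6:

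| k | Death as event | Censored at day 0 |
|---|---|---|
| 0 | 70.0% | 70.0% |
| 1 | 65.0% | 68.4% |
| 2 | 60.0% | 66.7% |
| 3 | 55.0% | 64.7% |
| 4 | 50.0% | 62.5% |

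Over m = 4 to 8 and k = 1 to 4 the gap runs from 2.9 points (k = 1, m = 8) to 15.0 points (k = 4, m = 4).

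**The same factor at Week 24.** Take 2 early deaths, 6 PD at the first scan, 6 PD at the second and 6 subjects progression-free. Deaths as events give 6/20 = 30.0%. Censored at day 0, the rate is 12/18 x 6/12 = 33.3%. The ratio is again 1.111.

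**Unscanned death after the landmark.** Take 6 PD at Week 8 and one subject never scanned who dies on day 70. As an event, this subject is still at risk and event-free at Week 8, so S = 14/20 = 70.0%. Censored at day 0, S = 13/19 = 68.4%. The direction reverses.

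**Intervals without censoring.** At 12/20 = 60.0% the two methods give the same estimate:
- Clopper-Pearson: 36.1% to 80.9%
- Kaplan-Meier, Greenwood variance, untransformed: 38.5% to 81.5%
- Kaplan-Meier, log-log: 35.7% to 77.6%

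**Intervals with censoring.** Take 2 early deaths counted as events, 6 PD at the first scan, 3 subjects censored there, 3 later PD and 6 progression-free at Week 24.
- Kaplan-Meier: 18/20 x 12/18 x 6/9 = 40.0%, log-log 17.7% to 61.6%
- Binomial, censored subjects as failures: 6/20 = 30.0%, 11.9% to 54.3%
- Binomial, censored subjects dropped: 6/17 = 35.3%, 14.2% to 61.7%

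**The case against.** By convention, censoring applies only to subjects without an event, and much of the plan points that way. The event row takes everyone who died. SAP 3.1 and Protocol 4.2.2 group subjects as died or progressed, surviving without progression, or lost to follow-up. The discontinuation rule and SAP 7.6 spell the condition out. Applied literally to the rule on undocumented progression, the wording would censor every death without PD and empty the death clause of the definition, so a programmer is unlikely to choose that reading. SAP 4.2 can also be read as support, since it treats a death as an observed outcome, though only for membership of the per-protocol set.

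This is persuasive on intent but does not close the gap. The no-assessment rule, unlike the other, can be applied literally without emptying the definition, because deaths after a scan would still count. It then looks like a specific rule overriding a general one. Writing the exception in some places and omitting it in others leaves the question open.

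On the interval, SAP 7.7 and the absence of a binomial interval from 7.4 favour Kaplan-Meier. That stands. What remains is the explicit binomial instruction in SAP 3.1 and Protocol 4.2.2, which could also be read as asking for both intervals. A binomial interval is unsuitable for a rate with censoring before the landmark.

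**Conclusion.** Wrong as written, and minor. Two censoring rules omit an exception that the event definition requires, and one rate has two prescribed interval methods. The size of the first depends entirely on the number of deaths before the first scan: none at k = 0, and 60.0% against 66.7% at k = 2 of 20. The factor 20/(20-k) holds for deaths before both the first scan and the landmark with no earlier censoring.

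Three stronger readings are tempting but not supported:
- A reader might infer that literal censoring can only raise the rate. The day-70 example (68.4% against 70.0%) shows otherwise for unscanned deaths after the landmark.
- A reader might infer that the curve is to be read at exactly 56 and 168 days, so that PD found late within the visit window is missed. No passage says so. SAP 2.2 ties Weeks 8 and 24 to Cycle 3 Day 1 and Cycle 7 Day 1, Protocol 4.2.1 ties the rates to those visits' assessments, and SAP 3.3 analyses visits as collected in the eCRF. The exact day is missing detail, not an error.
- A reader might infer a threat to the trial's conclusions. The 8- and 24-week PFS rates are secondary and descriptive. No decision rule or primary safety conclusion rests on them.

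**What to change.** (a) In SAP 7.4, limit the no-assessment rule, the rule on undocumented progression and the missing-assessment row to subjects alive without PD or clinical progression. Every observed death without prior PD is then an event. Match Protocol 4.2.1.4 if the protocol is amended.

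(b) In SAP 3.1, remove the PFS rate from the binomial-interval sentence, leaving it for ORR and DCR. Report the Kaplan-Meier estimate with its own interval, consistent with SAP 7.7. Match Protocol 4.2.2 if amended.

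The cost is a few words in the SAP and minor programming, with no new data. A protocol amendment would need the approvals in Protocol 7.2.5, but it need not delay the correction: SAP 1.0 lets the SAP set out differences from the protocol and lets later changes be described in the study report. The downside is that PFS rates may be slightly less favourable than under the literal rule.

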  - Total bilirubin  $\leq 5$  times ULN that downgrades to Grade  $\leq 2$  ( $\leq 3$  times ULN) within 7 days after onset, whereby maximal supportive care, including systemic corticosteroids, is permitted.
  - Grade  $\geq 3$  neutropenia that (1) is not associated with fever or systemic infection, (2) does not require medical intervention, and (3) improves to Grade 2 within 7 days.
  - Grade 3 and 4 lymphopenia.
  - Grade 3 thrombocytopenia that (1) is not associated with clinically significant bleeding, (2) does not require medical intervention, and (3) improves to Grade 2 within 7 days.
  - Isolated Grade 3 electrolyte abnormalities that are not associated with clinical signs or symptoms and are reversed with appropriate maximal medical intervention within 3 days.
  - Any pre-existing laboratory abnormality that deteriorates to Grade 3/4, but where the increment of deterioration is considered not clinically significant by both investigator and sponsor.
  - Grade 3 or 4 asymptomatic increases in amylase or lipase levels for which appropriate evaluation shows no clinical evidence of pancreatitis.

Immune-related AEs (irAEs) are defined as AEs of immune nature (i.e., inflammatory) in the absence of a clear alternative etiology. In the absence of clinical abnormality, repeat laboratory testing will be conducted to confirm significant laboratory findings prior to designation as a DLT.

While rules for adjudicating DLTs are specified above, an AE that is Grade < 3 or listed as exempt above may also be defined as DLT after consultation with the sponsor and Investigators, based on the emerging safety profiles of durvalumab, tremelimumab, and BI 1361849. Likewise, subjects who become not evaluable for DLT, because they discontinued or interrupted treatment due to toxicities other than DLTs, may be counted as DLT subjects, if the toxicities cannot be managed in accordance with the dosing modifications described in Section 3.1.8.

Subjects who experience a DLT will be discontinued from study treatment and will enter the On Study and Post Study Follow-up (see Section 3.1.16). However, if it is in the best interest of the subject, the Investigator, subject and Sponsor may agree to continue treatment with BI 1361849.

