### 3.1.10 Subject Withdrawal from Treatment or from Study

A subject will be **withdrawn from study treatment** for any of the following reasons:

1. Withdrawal of consent for further treatment
2. Pregnancy or intent to become pregnant
3. DLT at any time (see Section 3.1.9)
4. Progressive disease requiring alternative systemic treatment
5. Significant protocol violation or noncompliance that, in the opinion of the Investigator or Sponsor, warrants withdrawal
6. Development of intercurrent, non-cancer-related illnesses or complications that prevent either continuation of therapy or regular follow-up
7. Best medical interest of the subject (at the discretion of the Investigator)

Discontinuation from receiving study treatment does not mean that the subject is withdrawn from the study. If applicable, subjects who are withdrawn from study treatment should undergo the planned On Study Follow-up procedures (see Study Flowchart, Section 3.2), followed by the Post Study follow-up period (see Section 3.1.16).

A subject will be **withdrawn from the study** for the following reasons:

1. Best medical interest of the subject at the discretion of the Investigator
2. Initiation of alternative anticancer therapy (marketed or investigational)
3. Withdrawal of consent for all follow-up
4. Lost to follow-up
5. Death

Section 7.2.6 provides additional details regarding documentation for early subject withdrawal from study treatment and early withdrawal from study.

See also Sections 8.3 and 8.4 for subject withdrawal from treatment due to necessary dosing interruptions or discontinuations.

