## **4.2 Clinical Efficacy**

### **4.2.1 Endpoints and Assessment Methods**

Clinical efficacy will be assessed by irRECIST and RECIST 1.1 (see Section 8.5), measuring progression free survival (PFS) rate and objective response rate (ORR) at 8 and 24 weeks based on disease assessments at the scheduled Weeks 9 and 25 visits, as well as best overall response, disease control rate (DCR), duration of response (DoR), and overall survival (OS). Tumor disease assessments will be made at a minimum of every 8 weeks on study. See the sections below for additional details.

For the primary analysis, all efficacy endpoints will be assessed at the completion of the On Study Follow-up or completion of 12 cycles of therapy for the last subject.

PFS and OS will be updated at yearly intervals during the Post Study Follow-up and can be provided as addendums to the final report.

NOTE: Per Amendment 10.0, all post study follow-up will be discontinued as of 31 October 2021.

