#### **4.2.1.4 Progression-free Survival (PFS)**

PFS is defined as the interval between the date of first dose to the date of earliest determination of Progressive Disease (PD), or to the date of death, if PD does not occur. Subjects without documentation of progression at the time of the analysis will be censored at the date of last response assessment. Subjects with no tumor response assessment will be censored at the start date of the treatment. Subjects who discontinued treatment or withdrew from the study for reasons other than documented PD or death will be censored at the date of last response assessment prior to discontinuation or withdrawal.

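### PFS is censored when treatment stops for reasons other than PD or death, so PD seen later on study is dropped while DoR counts it; precedence for a death before the first scan is not stated

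*SAP*

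**What the plan says.** SAP 7.4 runs PFS from first dose to the earliest PD, including clinical progression, or to death if there is no PD. It then adds: "Subjects who discontinued treatment or withdrew from the study for reasons other than documented PD (including clinical progression) or death will be censored", the censoring date being the last response assessment before the stop. Protocol 4.2.1.4 has the same rule: "Subjects who discontinued treatment or withdrew from the study for reasons other than documented PD or death will be censored". Two further bullets in 7.4 censor subjects without documented progression at their last assessment, and subjects with no tumor assessment at the start of treatment. Neither makes an exception for deaths.

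SAP 7.6 runs DoR to the first of PD, clinical progression or death. It censors only responders who "did not lose it subsequently and were alive will be censored at the time of last available tumor assessment". It says nothing about stopping treatment.

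On follow-up, protocol 3.1.10 says: "Discontinuation from receiving study treatment does not mean that the subject is withdrawn from the study". Protocol 3.1.9 says: "Subjects who experience a DLT will be discontinued from study treatment and will enter the On Study and Post Study Follow-up". The flowchart (protocol 3.2) schedules scans every 8 weeks through On Study Follow-up, which ends 91 days after the last dose. Protocol 3.1.16 collects progression and survival dates after that, until 31 October 2021.

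On timing, protocol 4.2.1 says that for the primary analysis "all efficacy endpoints will be assessed at the completion of the On Study Follow-up" or of 12 cycles for the last subject, and that "PFS and OS will be updated at yearly intervals during the Post Study Follow-up".

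**The concern.** A subject who stops for toxicity remains on study and continues to be scanned. If a later scan shows PD, PFS ignores it. A later death is ignored too if the clause is applied as written, although its words on death leave room to count it.

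This sits badly with the rest of the plan. The yearly PFS updates take place when every subject is off treatment, yet a subject who stopped early for a non-PD reason can never change in them. For symptomatic deterioration, protocol 8.5 asks sites to document progression after treatment stops. DoR and PFS can also give conflicting accounts of one subject. Starting new anticancer therapy is a study-withdrawal reason (protocol 3.1.10), so it censors PFS only by implication and does not censor DoR at all.

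For a death before the first scan, the definition and the event row in 7.4 give an event, while the no-assessment bullet gives censoring at day 1. No order of precedence is stated.

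At stake is how the 8- and 24-week PFS rates are read. If those who stop do worse than those who continue, censoring them raises the estimates; if they do better, it lowers them; if stopping is unrelated to prognosis, the shift is about zero.

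**Working it through.** No figure in the plan depends on these rules, so there is none to reproduce. All subject counts and rates below are assumptions, because the documents give no discontinuation or early-death rates.

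**Are later progressions observed?** Scans fall at Weeks 9, 17 and 25, that is Days 57, 113 and 169 (protocol 3.2). With a last dose on Day 85, On Study Follow-up runs to Day 85 + 91 = Day 176. The Day 113 and Day 169 scans both fall inside it.

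**One subject under both rules.** PR on Day 57, confirmed Day 113, then a toxicity stop, then PD on the Day 169 scan.
- DoR (SAP 7.6): (169 − 57 + 1)/7 = 16.1 weeks, with an event.
- PFS (SAP 7.4): censored on Day 113, 113/7 = 16.1 weeks, with no event.

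PFS starts 8 weeks before the response, yet is no longer than DoR and omits the progression that DoR counts.

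**Worked Kaplan-Meier count, n = 20.** Five have PD on Day 57. Three of the other 15 stop for toxicity after the Day 85 dose. Of the 12 who continue, 2 have PD on Day 113 and 1 on Day 169.
- Current rule: the three are censored at Day 57, so 24-week PFS = 15/20 × 10/12 × 9/10 = 56.25%, whatever later happens to them.
- Using their follow-up scans, with k of the three having PD on Day 113: 15/20 × (13 − k)/15 × (12 − k)/(13 − k) = 60%, 55%, 50%, 45% for k = 0, 1, 2, 3.
- Current minus revised: about −4 to +11 points.

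**Average shift by simulation.** There were 200,000 subjects per scenario, with exponential PFS, median 4 months, 15% of events deaths, and 20% assigned to stop, spread over Day 8–168 (9–17% stop before an event). The hazard ratio (HR) compares stoppers with the rest. The revised rule counts PD on scans up to last dose + 98 days (91 plus the 7-day window) and counts all deaths. Current minus revised, in points:

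| Stopper HR | 0.5 | 1 | 1.5 | 2 | 3 |
|---|---|---|---|---|---|
| 24 weeks | −2.7 | −0.2 | +1.2 | +1.9 | +2.5 |
| 8 weeks | −0.7 | −0.1 | +0.4 | +0.8 | +1.5 |

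Ranges over HR 0.5 to 3 in other scenarios:

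| Scenario | 24 weeks | 8 weeks |
|---|---|---|
| 10–30% assigned, median 3–6 months | −4.4 to +4.5 | −1.2 to +2.3 |
| Censoring at new therapy kept; every stopper starts it 14–84 days after stopping | −1.5 to +1.6 | −0.6 to +1.3 |
| Every stop before Day 57, 20% assigned | −3.2 to +4.9 | −2.7 to +5.7 |
| Every stop before Day 57, 30% assigned | −4.9 to +7.3 | −4.1 to +8.4 |

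**Death before the first scan.** Take one death before Day 57 and five PDs at the first scan. With the death as an event, 8-week PFS = 14/20 = 70%. Censored at day 1, it is 14/19 = 74%.

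**Scale.** The exact interval for 8/20 in protocol 3.1.6 is 19% to 64%.

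**Replacement.** Protocol 3.1.11 and SAP 11.1 allow replacement of subjects not evaluable for the PFS rate. This restores precision but does not remove the shift. Replaced subjects who were dosed stay in the ITT population, and replacements come from the same population, so the expected share of stoppers is unchanged.

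**The case against.** The strongest reply is that dropping later PD is only the literal reading. The PFS definition and the event row in 7.4 carry no treatment-stop limit, so a programmer might apply the discontinuation clause only where no later PD exists. That reading is possible, but nothing gives it precedence over a clause that names these subjects and fixes a censoring date before the stop. A separate bullet already censors subjects without documented progression, so on that reading the clause would only move their censoring date back. If it is the intended reading, it has to be written.

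Several narrower points are fair:
- After a DLT, vaccine may continue by agreement (protocol 3.1.9), so a DLT does not always end treatment. Protocol 8.3 and 8.4 list other toxicity stops.
- The yearly updates still serve subjects who complete treatment.
- SAP 7.4 has a row counting subjects who start alternative therapy. It directly follows the list of censored subjects and may belong to it, but it gives no censoring date and has no counterpart in 7.6.
- SAP 4.2 lists death among disease assessments, but only to define the per-protocol population.
- The DoR mismatch affects only responders who stop for a non-PD reason and later progress.

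Censoring at discontinuation can also be a deliberate choice, and both documents prespecify it. That supports keeping it as a sensitivity analysis. It does not explain why PFS and DoR differ. Finally, the average shift is small, its sign is unknown, and the endpoint is descriptive. All of that stands and limits how much weight the point carries.

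**Conclusion.** The concern holds. The PFS rule, as written in both documents, discards progressions that the protocol arranges to observe, and SAP 7.6 counts those same progressions in DoR. The early-death part is a missing precedence rule; 7.4 does not say that deaths are censored.

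Under the assumed inputs, with stops spread over the first 24 weeks, the average effect is within about 4.5 points at 24 weeks and 2.3 points at 8 weeks, in either direction. A single arm of 20 can move more, as the worked count shows. The documents do not indicate whether stoppers do better or worse, so the direction is not known. The shift is small beside the n = 20 interval and no hypothesis test depends on it. It should be fixed because it affects how the PFS rates are read and makes two endpoints disagree for the same subject.

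**What to change.** In SAP 7.4 and protocol 4.2.1.4:
- Count documented PD, including clinical progression, or death as a PFS event whether or not study treatment has stopped, in line with SAP 7.6.
- State that death without a scan is an event on the date of death and takes precedence over the censoring bullets.
- Limit censoring at treatment start to subjects who are alive with no post-baseline assessment, and censor other event-free subjects at their last evaluable assessment.
- State how new anticancer therapy is handled and apply it the same way to PFS and DoR. Censoring at its start may remain primary.
- Report the current discontinuation-censoring rule as a sensitivity analysis.

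The cost is wording in two sections, one line in SAP 7.6 and one sensitivity table, all on data the protocol already collects. PFS may look slightly less favourable. Progression dates from 6-monthly contact or outside records are less precise than scheduled scans and should be flagged.
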